## **15.0 Risks to Subjects**

- 15.1 Injury during physical activity. There is a chance for physical injury during physical activity such as muscle and joint sprains or strains, muscle cramps, and inflammation. These risks will be monitored and minimized by conducting a warmup as a part of each exercise class.

## **16.0 Potential Benefits to Subjects**

- 16.1 Individual subject. Benefits to individual participants include the well-established benefits of physical activity engagement, including increased fitness and functional capacity, cognitive improvements, and mood improvements. Participants may also benefit from engaging in a group setting during the classes.
- 16.2 Population. The information from this study will aid in the understanding of the role of choreographed exercise in physical activity enjoyment and fitness and cognitive improvements for this population. This study may provide guidance for future interventions designed to increase physical activity for this population, with the goal of increasing cardiovascular fitness and reducing risk of Alzheimer's disease.

## **17.0 Data Management and Confidentiality**

17.1 The primary aim of this study is to determine the preliminary feasibility and effectiveness of a 12 week remote intervention. As this is a pilot study, the sample size is not sufficient to determine true intervention effectiveness, however it will provide sufficient data to guide future studies. Other studies with similar design included between 12 and 30 participants [27, 50, 51], which is how the sample size for this pilot project was derived.

- Pre and post scores for the Physical Activity Enjoyment Scale, 6 minute walk, and cognitive assessments will be compared using paired sample t tests. Effect sizes (Cohen's d) will also be calculated.

17.2 This study will use a REDCap database for data management. Paper copies from the energy expenditure assessments will be stored in a locked file cabinet inside a locked office that is only accessible by authorized study personnel.

Data access: Only the study team at The University of Kansas Medical Center (i.e., principal investigator, co-investigators, study coordinator, and research assistant) will have access to the study folder and REDCap database.

17.3 To assure data collected are accurate and consistent, the same research assistants will complete data collection for all participants. Data entered into REDCap by the research staff will undergo data validation checks by another member of research staff not involved in data entry.

## **18.0 Provisions to Monitor the Data to Ensure the Safety of Subjects**

18.1 An adverse event (AE) is any unfavorable medical occurrence in a human subject participant including any abnormal sign, symptom, or disease that is temporally associated with the participants' involvement in the research even if it is not considered related to the participation in the study. Signs and symptoms that are consistent with normal exercise including work-related dyspnea, fatigue, sweating, or light soreness of muscles will not be considered AEs. A serious adverse event (SAE) is defined as any adverse event that results in death, a life-threatening event, inpatient hospitalization, or a permanent disability.

AEs and SAEs will be tracked by the research assistant, study coordinator, or principal investigator for each exercise session. These events will be tracked on an adverse event form in REDCap and will include any events that occurred during or after the exercise sessions. Each reported event will be documented if it meets the criteria for an AE or SAE. Documentation will include a description of the event, when and how it happened, and any documentation to determine event severity and relatedness to the research study. Follow-up for each occurrence will be initiated by the study team and continued until the event is resolved. The principal investigator for the study will review and evaluate adverse events within 72 hours and a summary of these events can be provided to the IRB on an annual basis. Deaths will be reported within 24 hours and unanticipated SAEs will be reported within 48 hours to the IRB. All other SAEs will be reported semi-annually.

Muscular or joint-related injuries and cardiovascular events due to vigorous physical activity are the primary risks for this study, but this risk is attenuated with the warm up built into the program of each class. This risk is also minimized by the rest periods, if needed. The data safety monitoring plan will include close monitoring of each participant during the exercise testing at baseline and week 12 by the research assistants who have exercise testing experience in special populations, including those with Down syndrome. The principal investigator will be responsible for the immediate reporting of excessive or serious events to the IRB at The University of Kansas Medical Center. Safety reports will be compiled by the principal investigator throughout the study and the frequency of data review will differ based on the type and availability of the data collected and the perceived risk level. Data review will also include quarterly review of subject accrual (e.g., demographics, inclusion/exclusion) and compliance to the protocol; monthly review of adverse event rates; and semi-annual review of the stopping rules.

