## **9.0 Study Timelines**

- 9.1 The intervention will last for 12 weeks. Baseline testing visits will occur within two weeks of the start of the intervention and week 12 visits will occur within 2 weeks of the program ending. Based on these parameters, study enrollment will last up to 16 weeks including pre, and post intervention testing.
- 9.2 Participants will be recruited in two cohorts of 10 participants each. It is projected for the first cohort to begin in the Fall of 2024, with recruitment taking place in summer and early fall. The second cohort will begin in early 2025, with ongoing recruitment efforts starting during the delivery of the intervention to the first cohort.
- 9.3 Primary analyses will be completed in Summer 2025, following the conclusion of the second cohort. This will allow ample time for data collection and processing from both cohorts.

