## **14.0 Withdrawal of Subjects**

- 14.1 Participants will be withdrawn from the research without their consent if an SAE occurs which is deemed by the study team and PI and unsafe for continued participation.
- 14.2 Upon withdrawal from the study, all research activities will cease, and no additional data will be collected. Participants will no longer be able to attend the weekly exercise classes.

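### Section 18.0 sets two incompatible reporting times for an anticipated non-fatal SAE, and 14.2 ends data collection at withdrawal although 18.1 requires follow-up to resolution

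*Protocol*

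**What the plan says.** **Reporting.** Section 18.1 of the protocol sets tiers. For the first two it says: "Deaths will be reported within 24 hours and unanticipated SAEs will be reported within 48 hours to the IRB". For the remainder: "All other SAEs will be reported semi-annually". This last sentence names no recipient; the IRB, named in the sentence before it, is the probable one. A later paragraph of section 18.0, on risks and data review, says: "The principal investigator will be responsible for the immediate reporting of excessive or serious events to the IRB". It makes no distinction between anticipated and unanticipated events. The protocol does not define *unanticipated* or *excessive*.

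**Risks.** The same later paragraph states: "Muscular or joint-related injuries and cardiovascular events due to vigorous physical activity are the primary risks for this study". Section 15.1 gives only musculoskeletal examples: "There is a chance for physical injury during physical activity such as muscle and joint sprains or strains, muscle cramps, and inflammation".

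**Withdrawal and follow-up.** Section 14.1 says: "Participants will be withdrawn from the research without their consent if an SAE occurs". The sentence goes on to limit this to an SAE that the study team and principal investigator judge to make continued participation unsafe. Section 14.2 then says: "Upon withdrawal from the study, all research activities will cease, and no additional data will be collected". Section 18.1 requires the study team to follow every reported event until it resolves and makes no exception for people who have left the study.

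The SAP does not mention adverse events, so it settles neither point.

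**The concern.** Each pair of rules governs the same situation and asks for different things. Staff who treat an anticipated hospitalization as semi-annual comply with one sentence of section 18.0 and break another. Staff who close the record of a participant withdrawn after an SAE comply with 14.2 and break 18.1.

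The reporting time matters because section 18.0 names no recipient of event reports outside the study team other than the IRB. If the semi-annual sentence is followed alone, the only outside reviewer could learn of a hospitalization after the participant has finished. The follow-up rule matters because it bears on the people whose outcome is of most interest, those removed for safety. Section 2.1 lists adverse events among the data to be collected throughout the intervention, so a missing outcome would weaken what this pilot can report on safety.

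**Working it through.** The plan gives no figure to reproduce. The check is a comparison of the text, with one calculation for scale.

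**Step 1. Reporting time by type of SAE.** Inputs: the tiers in 18.1 and the immediate-reporting sentence later in 18.0.

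| Type of SAE | Time in 18.1 | Time later in 18.0 | Does meeting the 18.1 time also meet the other? |
|---|---|---|---|
| Death | 24 hours | Immediate | Yes, on a loose reading of immediate |
| Unanticipated, non-fatal | 48 hours | Immediate | Yes, on a loose reading of immediate |
| Anticipated, non-fatal | Semi-annual | Immediate | No |

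The conflict lies in the third row. Immediate can serve as shorthand for one or two days, but not for half a year.

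**Step 2. Scale of the gap.** Inputs: semi-annual taken as 26 weeks (assumption); maximum time on study from section 9.1, "study enrollment will last up to 16 weeks including pre, and post intervention testing".

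- Longest wait under the semi-annual sentence: 26 × 7 = 182 days.
- Maximum time on study: 2 weeks before + 12 weeks of classes + 2 weeks after = 16 weeks; 16 × 7 = 112 days.
- Difference: 182 − 112 = 70 days, or 10 weeks.

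At worst, then, an SAE on any study day could be reported after that participant has left. This is an upper limit on the calendar gap. It does not measure risk.

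**Step 3. Withdrawal against follow-up.** Take a participant hospitalized after a class whose continued participation is judged unsafe.

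1. 14.1 withdraws the participant.
2. 14.2 ends all research activities and data collection from that point.
3. 18.1 requires follow-up until the event resolves. Events are tracked on a REDCap adverse event form, so on a plain reading a follow-up entry is further data collection.

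Steps 2 and 3 cannot both be followed literally if the event is unresolved at withdrawal. 14.2 is not limited to withdrawals under 14.1, so the same holds for anyone who leaves with an open adverse event. The documents give no SAE rate and no time to resolution, so no expected number of affected events is computed.

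**The case against.** The strongest reply is that the rules can be met together. The team can report every SAE promptly and list it again in a semi-annual report, and can treat 18.1 as the specific rule that prevails over the general sentence in 14.2. 14.2 can also be read as covering study procedures and outcome data only. These readings are sensible, but the protocol states none of them, and a reader who follows the semi-annual sentence or 14.2 literally breaks another stated rule. The consent pages are not in the copy reviewed, so wording there on follow-up after withdrawal cannot be checked.

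Other protections also stand: review by the principal investigator within 72 hours, monthly review of adverse event rates, medical clearance from the participant's physician, and removal for safety concerns. They limit the harm, but they do not say when the IRB is told.

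A reader might infer three stronger claims that the documents do not support.

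- **One SAE carries three deadlines.** In 18.1 the 48-hour and semi-annual tiers exclude each other. Once classified, a non-fatal SAE has two times: its tier and immediate.
- **Section 15.1 makes a cardiac event unanticipated.** The list in 15.1 is introduced as examples and does not set what is anticipated. Section 18.0 names cardiovascular events as a primary risk, so the protocol read as a whole anticipates them. The lack of a definition remains a gap.
- **The ratio of 182 days to 48 hours shows the size of the danger.** It compares calendar intervals only, and those two limits apply to different tiers.

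Finally, tiering by expectedness is a legitimate choice. A single time limit for all SAEs is one acceptable repair, and the documents do not show it to be required.

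**Conclusion.** The point holds on two counts. An anticipated non-fatal SAE is subject to both a semi-annual and an immediate reporting rule, and 14.2 conflicts with 18.1 for any adverse event still open at withdrawal. At worst the slower reporting route runs to about 182 days, 70 days beyond the longest time a participant can be on study. This assumes that semi-annual means 26 weeks, that the semi-annual report goes to the IRB, and that the team acts on that sentence and not on the immediate one.

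The consequence is confined to safety oversight and the completeness of the safety record. Sample size, feasibility outcomes and efficacy analyses are untouched. With 20 participants the number of events may be small, but the documents give no rate. Nothing in them shows that an SAE was reported late or lost to follow-up. The correction is worth making because it costs little and removes a choice that staff should not have to make during an event.

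**What to change.** **Reporting.** State in section 18.0 that the prompt rule governs all SAEs: deaths within 24 hours, and other SAEs promptly under IRB policy, for example within the existing 48 hours. Keep the semi-annual report as a cumulative summary only. If a slower tier for anticipated SAEs is intended, limit the immediate-reporting sentence to deaths and unanticipated SAEs, and define *unanticipated* against the risk list in section 18.0. In either case, name the recipient of the semi-annual report.

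**Withdrawal.** Amend 14.2 so that adverse events that began before withdrawal are followed to resolution unless the participant or guardian declines.

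**Cost.** A short amendment with IRB review, possibly a change to the consent wording, and a few follow-up contacts. The existing REDCap form can be used.

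**If the study is complete.** Section 9.2 projected the cohorts for Fall 2024 and early 2025, and the SAP, dated November 2025, is written in the past tense. If conduct has ended, the wording serves any successor protocol. The action now is to check that every SAE reached the IRB promptly and that events in withdrawn participants were followed to resolution, and to report any that were not.

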## **19.0 Provisions to Protect the Privacy Interests of Subjects**

- 19.1 Any data, forms, reports, video recordings, and other records that leave the site will be identified only by a participant identification number (Participant ID, PID) to maintain confidentiality. All records will be kept in a locked file cabinet. All computer entry and networking programs will be done using PIDs only. Information will not be released without written permission of the participant, except as necessary for monitoring by IRB, the FDA, the NIA, and the OHRP.
- 19.2 All research staff have training to work with adults with DS. This training includes describing research to participants, ensuring participant safety, and ensuring participant comfort. Participants and caregivers are continually reminded that their participation in any study procedure is voluntary.

## **20.0 Compensation for Research-Related Injury NA**

## **21.0 Economic Burden to Subjects**

- 21.1 Participants are responsible for providing their own transportation to and from the research center for testing visits.

## **22.0 Consent Process**

22.1 Consenting Procedure Remote video chat sessions (Zoom) or in person consent meetings depending on participant preference, will be scheduled with participants, caregivers, and their legal guardian (if applicable) deemed to be initially eligible to describe the project in detail, answer questions, verify eligibility, and to obtain participant consent or, if the participant is not their own legal guardian, guardian consent and participant assent. Medical consent from the participant's physician will also be obtained prior to enrollment in the study. The physician will receive a description of the study, and a request for medical clearance to participate in the physical activity.

22.2 For remote video chat sessions (Zoom): Prior to the consenting session, the participant will be sent the consent form and cover letter through Kansas University Medical Center's (KUMC) secure email system. Study staff will set up a virtual Zoom meeting that allows for remote video chat. Study staff will "share screen" the consent document and walk through each section, noting questions that arise, and answer these

questions fully. The signed and dated consent form will be submitted online through REDCap.

22.3 For in person consent meetings: study staff will meet at a mutually chosen location to meet with the potential participant, study partner, and legal guardian (if applicable). They will review the study with them, read the informed consent to them, and answer any questions. The participant will be allowed to keep the consent form and read over on their own and join at a later time. We will collect informed consent from participants, or if a participant is not their own legal guardian, we will collect participant assent and legal guardian/surrogate decision maker consent. We will obtain assent away from family members to make sure participants don't feel like they have to be in the study.

### ***Cognitively Impaired Adults***

The consent process for participants with known or suspected cognitive impairment includes an assessment of the capacity to provide consent for oneself. If the participant does not demonstrate capacity to consent, written consent will be obtained from the proper surrogate decision-maker, following Kansas law for DPOA and next-of-kin. In these instances, the participant's assent will be obtained and documented as well. Each team member qualified to consent has training on the ADRC SOP regarding consenting participants with impaired decision making and will follow the guidelines in the ADRC SOP Consenting Cognitively Impaired Participants to determine if subject is capable of consenting. In addition, all team members have experience consenting individuals with either DS or dementia or AD previously.

### ***Adults Unable to Consent NA***

## **23.0 Process to Document Consent in Writing NA**

### **24.0 Setting**

- 24.1 Potential research participants will be identified and recruited through contact with local community agencies serving adults with DS, case managers, and CDDOs by mail or email, provide presentations at CDDO meetings, and text for CDDO newsletters describing the project.
- 24.2 All research activities will be performed at the Division of Physical Activity and Weight Management or Kirmayer Fitness Center on campus of KUMC, with the exception of the energy expenditure assessment. Since classes are held remotely, research staff will travel to participant homes or wherever they engage with these classes to perform this assessment.

### **25.0 Resources Available**

- 25.1 The Division of Physical Activity and Weight management currently maintains a listserve of over 230 contacts in the community that serve adults with Down syndrome. The division has been able to successfully recruit cohorts of 20 participants at a time for a previous Down syndrome physical activity study within a 1-year time frame.
- 25.2 KUMC Clinical Weight Management (Kirmayer Building) is a 5,000 ft facility, that originally served as a Sports Medicine Clinic and has been occupied by The Division of Physical Activity and Weight Management

since the spring of 2012. This facility includes the following: an 800 ft waiting room, 4 staff offices, an office suite for project coordinators, 4 exam rooms ( ~ 120 ft), a conference room, and an exercise room for conducting supervised aerobic or resistance exercise with adjacent handicap accessible locker rooms for both men and women, and extensive audio and video entertainment packages to facilitate participant compliance.

- 25.3 All assessments will be completed by appropriately trained staff. Baseline and 12-week outcomes will be assessed at our facilities at KUMC. Staff will receive refresher training and complete reliability assessments for all physical measures 2-3 times/yr. All dance exercise sessions will be video recorded and 20% will be reviewed by study staff. The content delivered during each session will be compared with a checklist of scheduled content. Interventionists presenting < 80% of the scheduled content for any session will receive additional training and will be dismissed if the problem recurs.

Statistical Analysis Plan

Official Title:

Decreasing Alzheimer's Risk Through oNline Choreographed Exercise – Down Syndrome

NCT Number: NCT06537648

Date: November 6th, 2025

Statistical Analysis Plan

Due to the pilot nature of this study, no formal hypothesis testing was conducted. Descriptive statistics were used to summarize all outcomes. Continuous variables are presented as mean \pm standard deviation, and categorical variables are presented as frequency (percentage).

Intervention adherence was calculated as the average percentage of classes attended across the 12-week intervention period. Retention was defined as the percentage of enrolled participants who completed the study through the final assessment timepoint.

Energy expenditure data (METs) from physical activity assessments were averaged across 30-second epochs for each participant and displayed using boxplots to visualize individual-level variability and distribution.

All data processing and statistical analyses were conducted using R software (version 4.3.2).

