## 2.0 Objectives

2.1 Adults with Down syndrome (n=20) will participate in a 12 week, remotely delivered choreographed exercise intervention. Classes will take place 2 times per week and be 35 minutes in length. Prior to the start of the intervention (baseline) and at the conclusion of the intervention (week 12), aerobic fitness (6-minute walk test), cognitive function (modified cued recall), and physical activity enjoyment will be assessed. Attendance, retention, and adverse events will be collected on an ongoing basis throughout the intervention. The purpose of this pilot project is to assess the usability, feasibility, and preliminary effectiveness of a remotely delivered choreographed exercise intervention for the prevention of Alzheimer's disease in adults with Down syndrome. This project will address the following aims:

- Aim 1: Assess the feasibility of a 12 week, remotely delivered group dance intervention
- Aim 2: Assess changes in aerobic fitness and cognitive function in response to a 12 week remotely delivered group dance intervention
- Aim 3: Assess the intensity and total energy expenditure of remotely delivered group dance sessions

2.2 We hypothesize the following:

- Aim 1: Session attendance and participant retention will be  $\geq 80\%$ , and physical activity enjoyment (measured using the Physical Activity Enjoyment Disabilities Scale) will increase from baseline to week 12
- Aim 2: We expected significant improvements in aerobic fitness and cognitive function across the 12 week intervention
- Aim 3: Energy expenditure will exceed  $\geq 3.0$  METs during the exercise sessions and average heart rate will reach 65 % of age-estimated maximal heart rate

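### The SAP drops the protocol's paired t tests and Cohen's d for enjoyment, 6-minute walk and cognition without saying so, and puts no measure of uncertainty in their place

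*SAP*

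**What the plan says.** Protocol section 17.1 sets out the analysis of the three pre-post outcomes: "Pre and post scores for the Physical Activity Enjoyment Scale, 6 minute walk, and cognitive assessments will be compared using paired sample t tests". It adds: "Effect sizes (Cohen's d) will also be calculated". The paragraph just above in the same section carries the pilot caveat: "As this is a pilot study, the sample size is not sufficient to determine true intervention effectiveness".

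The hypotheses in protocol section 2.2 rely on these comparisons. For Aim 2: "We expected significant improvements in aerobic fitness and cognitive function across the 12 week intervention". For Aim 1, besides the attendance and retention thresholds, enjoyment "will increase from baseline to week 12".

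The SAP takes a different position: "Due to the pilot nature of this study, no formal hypothesis testing was conducted", followed by "Descriptive statistics were used to summarize all outcomes". Continuous variables get a mean and SD. The SAP defines adherence, retention and the handling of METs. It does not name enjoyment, 6-minute walk or cognition, and contains no change score, paired comparison, effect size, standard error or confidence interval.

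On timing, protocol section 9.3 says: "Primary analyses will be completed in Summer 2025". The SAP is dated 6 November 2025 and written in the past tense.

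**The concern.** The two documents give different analyses for the same three outcomes, and the later one does not acknowledge the difference. The protocol's revision history has no entries, so the change is not recorded there either.

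Three things are at stake. First, the Aim 2 hypothesis is worded in terms of significance and, under the SAP, receives no verdict. Second, changes in fitness and cognition (a secondary objective) and in enjoyment (part of the Aim 1 hypothesis) can be described by direction and size, but with no stated precision. Third, section 17.1 says the data are meant to inform later studies. Planning a later pre-post comparison needs the variability of within-person change, and the SAP does not promise it.

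**Working it through.** **The text.** The two plans compare as follows.

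| Item | Protocol 17.1 | SAP |
|---|---|---|
| Pre-post comparison of the three outcomes | Paired t tests | None; no formal testing |
| Effect size | Cohen's d (variant not stated) | Not mentioned |
| Confidence interval | Not mentioned | Not mentioned |
| SD | Of the change, implied by the paired test | Given, but not said whether per visit or of the change |
| Participants analysed | Those with both visits, implied by pairing | Not stated |
| Pilot status | Stated, and tests planned anyway | Given as the reason for not testing |

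Pilot status is common to both documents, so it cannot explain why one tests and the other does not. Cohen's d is an estimate, so a decision not to test does not account for its absence.

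**The size of the information loss.** The documents give no power, SD or effect size, so there is no stated figure to reproduce. What follows is an illustration.

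Inputs:
- From the protocol: 20 participants (section 12.1). The 80% retention threshold (section 2.2) gives 0.80 × 20 = 16 pairs.
- Assumed: a visit-to-visit difference of 0.30 baseline SD, equal SDs at the two visits, pre-post correlation r of 0.5, 0.8 or 0.9, and two-sided 95% intervals.

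*If the SD of change and the number of pairs are reported*, the half-width of the interval, in SDs of change, is t(0.975, n−1)/√n:
- n = 20: 2.093/4.472 = 0.468
- n = 16: 2.131/4 = 0.533

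*If only per-visit SDs are reported*, the SD of change must be inferred. With equal visit SDs it is √(2(1−r)) baseline SDs. At n = 16 the half-width in baseline SDs is 0.533 × √(2(1−r)), and the effect size in SDs of change is 0.30/√(2(1−r)).

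| Assumed r | SD of change / baseline SD | Half-width, n = 16 | 95% interval for 0.30 | Effect size in SDs of change | Paired t test p |
|---|---|---|---|---|---|
| 0.5 | 1.000 | 0.533 | -0.23 to 0.83 | 0.30 | 0.249 |
| 0.8 | 0.632 | 0.337 | -0.04 to 0.64 | 0.47 | 0.077 |
| 0.9 | 0.447 | 0.238 | 0.06 to 0.54 | 0.67 | 0.017 |

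All three rows would print the same visit means and SDs. With 20 pairs the half-widths are 0.468, 0.296 and 0.209 baseline SD, and p is 0.196, 0.047 and 0.007.

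**How far this depends on the 0.30.** With 16 pairs, a change below about 0.24 baseline SD gives an interval that includes zero at all three correlations, and a change above about 0.53 excludes zero at all three. Between those values the printed summaries do not settle the matter. The width of the interval is unknown whatever the change.

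**The case against.** The strongest reply is that leaving out p values is sensible in a single-arm feasibility study of 20 people, that it agrees with the protocol's own caveat about sample size, and that the SAP says openly that it did not test. That stands as a defence of not testing. It does not explain the missing Cohen's d or the silence about the protocol's plan.

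A second reply is that uncertainty is unrecoverable only if the SDs are per visit; with the SD of change and the number of pairs, a reader can derive the interval. That is correct. But the SAP promises neither, and under either reading it states no precision.

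Third, the protocol never promised confidence intervals, so asking for them goes beyond restoring its plan, and a 95% interval carries the same information as a two-sided 5% paired t test. Both points are fair: the interval is a recommendation. It needs only the mean change, SD of change and number of pairs that the planned t test already uses, and it presents the result as an estimate, which suits a pilot.

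Finally, the impact is limited. The primary objective is feasibility, and a mean alone can show whether enjoyment rose. The loss falls mainly on the secondary outcomes. As to timing, a projected analysis date and a document date do not show that results were seen before the choice was made, and no such inference is drawn here.

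**Conclusion.** The concern holds. The SAP omits two analyses that the protocol commits to, does not acknowledge the omission, and gives a reason that was already present when the analyses were planned. As written, the Aim 2 hypothesis goes unanswered and changes in three outcomes are reported without stated precision.

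The size depends on what is finally printed. With the SD of change and the number of pairs, the half-width follows directly: 0.47 SD of change with 20 pairs or 0.53 with 16. With per-visit SDs only, the half-width at 16 pairs could be anywhere from 0.24 to 0.53 baseline SD over correlations of 0.9 to 0.5. Those correlations, the equal visit SDs and the 0.30 are assumptions. The mismatch between the documents rests on none of them.

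This should be fixed, but it does not touch the attendance and retention results.

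**What to change.** In the SAP and the report, for each of enjoyment, 6-minute walk distance and the modified cued recall score, give the following in participants with both visits:
- the number of pairs;
- the mean within-person change (week 12 minus baseline) and its SD;
- the 95% confidence interval;
- Cohen's d, naming the SD used to standardise it.

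Then do one of two things about the t tests. Either report them, labelled exploratory, or list their removal as a dated deviation from protocol 17.1, with the reason and whether outcome data had been seen when the decision was made. Leave the Aim 2 hypothesis as written. Do not attribute any change to the intervention, because there is no control arm.

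The cost is some wording and a few lines of R on data already collected. The downside is that the intervals will be visibly wide.
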